9.4.2 Data Collection and Follow-up for Withdrawn Subjects.....	37
10 Study Device	37
10.1 Description	37
10.2 Treatment Regimen	38
10.3 Method for Assigning Subjects to Treatment Group	38
10.4 Preparation and Use of Study Device	38
10.5 Subject Compliance Monitoring	43
10.6 Prior and Concomitant Therapy	43
10.7 Packaging	43
10.8 Blinding	43
10.9 Receiving, Storage, Dispensing and Return	43
10.9.1 Receipt of Devices.....	43
10.9.2 Storage	43
10.9.3 Dispensing of Study Device.....	43
10.9.4 Return or Destruction of Study Device	44

11 Study Procedures	44
11.1 Visit 1	44
11.2 Visit 2	45
11.3 Visit 3	45
11.4 Visit 4	45
11.5 Visit 5	46
11.6 Visit 6	46
11.7 Visit 7	46
11.8 Visit 8	46
11.9 Visit 9	46
11.10 Visit 10	46
11.11 Visit 11	47
11.12 Visit 12	47
12 Statistical Plan	47
12.1 Statistical Methods	47
12.2 Subject Population(s) for Analysis	48
13 Safety and Adverse Events	48
13.1 Definitions	48
13.2 Recording of Adverse Events	50
13.3 Reporting of Serious Adverse Events and Unanticipated Problems	50
13.3.1 Investigator reporting: notifying the study sponsor	50
13.3.2 Investigator reporting:	51
13.3.3 Sponsor reporting: Notifying the FDA	51
13.3.4 Sponsor reporting: Notifying participating investigators	52
13.4 Stopping Rules	52
13.5 Medical Monitoring	52
13.5.1 Internal Data and Safety Monitoring Board or DSMP	53
14 Data Handling and Record Keeping	53
14.1 Confidentiality	53
14.2 Source Documents	53
14.3 Case Report Forms	54
14.4 Records Retention	54
15 Study Monitoring, Auditing, and Inspecting	54
15.1 Study Monitoring Plan	54
15.2 Auditing and Inspecting	54
16 Ethical Considerations	54
17 Study Finances	55
17.1 Funding Source	55
17.2 Conflict of Interest	55
18 Publication Plan	55

Study Summary

Title	A Pilot Study of Therapeutic Potential of Stem Cell Educator Therapy in Type 1 Diabetes
Short Title	SCE therapy in type 1 diabetes
Protocol Number	N/A
Phase	Pilot study
Methodology	Single arm, open-label
Study Duration	2 year
Study Center(s)	Hackensack University Medical Center
Objectives	
Primary Objective:
 
1) To assess the safety of SCE therapy in subjects with T1D. 
Secondary Objectives:
 
1) To assess the feasibility of SCE therapy in patients with T1D2) To evaluate preliminary efficacy of SCE therapy for improving β cell function in patients with T1D through 12 months.3) To evaluate markers of immune function in T1D patients after SCE therapy.
Endpoints	
Primary Endpoint
 
1) The occurrence of treatment-related adverse events 
Secondary Endpoints
 
1) Feasibility as determined by:
• The number of patients who were unable to complete SCE Therapy• The number of patients who are lost to follow-up prior to the 12-month follow-up visit.2) Preliminary efficacy as measured by
• Area under the C-peptide curve (AUC) over the first 2 hours of a 3-hour mixed meal tolerance test (MMTT)• Peak C-peptide levels over a 3 MMTT. Basal C-peptide levels Daily insulin requirements• Change in HbA1C levels over time• Daily insulin requirements• Changes in auto-antibody levels over time3) Measurements of immune markers at baseline, 1, 3, 6, 9, 12, and 24 months
Number of Subjects	10 subjects projected for the entire study
Diagnosis and Main Inclusion Criteria	Patients with T1D who meet the 2015 diagnosis standards of the American Diabetes Association and a blood test confirmed the presence of at least one autoantibody to pancreatic islet β cells.
Study Product, Dose, Route, Regimen	SCE-treated MNCs, single treatment, infused intravenously, one time infusion.
Duration of administration	3 – 5 hours
Statistical Methodology	All study data will be entered into a Microsoft Office Excel 2007 (Microsoft Corporation, Redmond, WA) and imported into SAS 9.2. The database will be validated in SAS to ensure any out range values are queried with the multiple sources and all data issues are resolved. Any P-value < 0.05 will be considered statistically significant. All data analysis will be performed using SAS 9.2 (SAS Institute Inc, Cary, NC).

6 Background

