8.1 General Design

This is a prospective, single arm, open-label, single-center pilot study to assess the safety, feasibility, and efficacy of SCE therapy for the treatment of patients with T1D. Up to 10 patients meeting eligibility criteria will be enrolled. Patients with T1D will be evaluated by the study principal investigator or co-investigators. Informed consent will be obtained at the initial screening visit (Visit 1). The initial screening visit will occur within 30 days of initiation of SCE therapy (**Table 3**). The second screening visit (Visit 2) will occur within 7 days of therapy. Subjects who meet all criteria will be scheduled for treatment. All enrolled subjects will receive treatment with the SCE system consisting of a single session of MNC collection by apheresis where 10 L (expected collection of ~10¹⁰ mononuclear cells) of blood will be processed on day -1. The MNC product will then be exposed over a 17-hour period of time to the SCE and on day 0 the product will be infused intravenously back to the patient. The infusion will take place in the Outpatient Transplant Facility at John Theurer Cancer Center (JTCC) or Inpatient at Hackensack University Medical Center (HUMC) on the stem cell transplantation or cellular therapy unit. The infusion will be performed according to the standard operating procedure, titled “Name of Procedure: Infusion of Non-Frozen Hematopoietic Stem Cell (HSC) Products and Cytotoxic T Lymphocytes”. After finishing the infusion, the patients will be hospitalized at the main hospital of Hackensack University Medical Center for a 24-hours post-infusion observation. If the patients show the stable blood glucose, blood pressure, temperature, and normal vital signs, they can be discharged from the hospital after 24 hours. Subjects will be treated sequentially, with a minimum of one week between subjects for the first three subjects. All treated subjects will attend a safety visit on Day +7 ± 1 day. Follow-up visits will occur on 1st, 3rd, 6th, 9th, 12th, and 24th month (± 5 days) post-therapy. Subjects will be instructed to record daily insulin doses, sugar levels, and physical activities. After receiving the SCE therapy, patients’ daily insulin doses will be monitored and adjusted their own endocrinologist.

[figure not shown]

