8.2 Primary Study Endpoint

The primary study endpoint will be the occurrence of treatment-related adverse effects. Adverse events that occur during therapy (especially those that necessitate temporary or permanent discontinuation of therapy) and over the 12-month follow-up period will be assessed.

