SAFETY ASSESSMENTS												
Phone call for safety follow-up					x	x				Continuous		
Concomitant med monitoring											Continuous	
Adverse Event monitoring												

9 Subject Selection and Withdrawal

This study will enroll a total of 10 subjects who meet the following eligibility criteria.

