13.1.4 Adverse Event Reporting Period

The study period during which adverse events must be reported is normally defined as the period from the initiation of any study procedures to the end of the study treatment follow-up.

For this study, the study treatment follow-up is defined as 30 days following the administration of study treatment. Serious adverse events should be reported to the local IRB and FDA within 7-10 days from the time of the event. Minor events can be reported in an annual report

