13.1.7 Post-study Adverse Event

All unresolved adverse events should be followed by the investigator until the events are resolved, the subject is lost to follow-up, or the adverse event is otherwise explained. At the last scheduled visit, the investigator should instruct each subject to report any subsequent event(s) that the subject, or the subject's personal physician, believes might reasonably be related to participation in this study. The investigator should notify the study sponsor of any death or adverse event occurring at any time (during the 6-month follow-up) after a subject has discontinued or terminated study participation that may reasonably be related to this study. The sponsor should also be notified if the investigator should become aware of the development of cancer or of a congenital anomaly in a subsequently conceived offspring of a subject that has participated in this study.

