13.2 Recording of Adverse Events

Based on our current clinical data in 200 subjects including Chinese and Caucasian patients, we did not see any significant adverse events during the treatment with SCE therapy, and follow-up studies after treatment for 4 years. No participants experienced any significant adverse events during the course of treatment. Most patients experienced mild discomfort during venipuncture and some soreness of the arm during aphaeresis, but discomfort and soreness resolved quickly following the conclusion of the procedure. No tumor formation and other safety concerns in all subjects after receiving SCE for 4 years.

At each contact with the subject, the investigator must seek information on adverse events by specific questioning and, as appropriate, by examination. Information on all adverse events should be recorded immediately in the source document, and also in the appropriate adverse event module of the case report form (CRF). All clearly related signs, symptoms, and abnormal diagnostic procedures results should be recorded in the source document, though should be grouped under one diagnosis.

All adverse events occurring during the study period must be recorded. The clinical course of each event should be followed until resolution, stabilization, or until it has been determined that the study treatment or participation is not the cause. Serious adverse events that are still ongoing at the end of the study period must be followed up to determine the final outcome. Any serious adverse event that occurs after the study period and is considered to be possibly related to the study treatment or study participation should be recorded and reported immediately.

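### The adverse-event periods are not reconciled: reporting is defined as 30 days, the primary endpoint as 12 months and visits run to Month 24, so second-year events fall in no stated analysis

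*Combined protocol and SAP*

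**What the plan says.** **The endpoint and its analysis.** The Study Summary words the primary endpoint as "The occurrence of treatment-related adverse events" and gives no window. Section 8.2 supplies one: events during therapy and those "over the 12-month follow-up period will be assessed". Section 12.1 plans counts and percentages of treatment-related events with exact 95% binomial intervals in the safety population. Neither 12.1 nor 12.2 gives a cut-off date.

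**Follow-up.** The Summary gives a study duration of 2 years. Section 8.1 states: "Follow-up visits will occur on 1st, 3rd, 6th, 9th, 12th, and 24th month (± 5 days) post-therapy". Table 3 schedules history, examination, blood count and chemistry at Month 24 and has a row for "Adverse Event monitoring". Section 13.2 requires that "At each contact with the subject, the investigator must seek information on adverse events", and also that "All adverse events occurring during the study period must be recorded".

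**Reporting periods.** Section 13.1.4 runs adverse-event reporting from the first study procedure to the end of study treatment follow-up, and then says: "For this study, the study treatment follow-up is defined as 30 days following the administration of study treatment". Section 13.1.7 asks for notification of possibly related events "during the 6-month follow-up" after a patient has left the study. Section 9.4.2 asks for 12 weeks of toxicity data after withdrawal.

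**The concern.** Safety is the primary objective, yet the protocol gives no single answer to two basic questions: for how long adverse events must be collected, and which of them count in the primary result.

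There are two consequences. First, a site that follows 13.1.4 could stop required reporting at 30 days, so the 12-month endpoint in 8.2 would rest on incomplete data for most of its window. Second, an event found at the Month 24 visit has no stated place in the results. One analyst could exclude it under 8.2, and another could include it because 12.1 and the Summary set no limit. The same data would then give two primary results.

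The shorter safety window is not explained. Section 12.1 carries C-peptide AUC and HbA1C, both secondary, to Month 24. Section 10.1 describes a static device with longer cell contact than the closed-loop system of the earlier trials, so long-term experience from those trials does not simply replace second-year data from this one.

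**Working it through.** The documents give no computed figure that depends on the safety window, so there is none to reproduce. The check sets the periods side by side and then sizes the difference.

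**1. Periods stated**

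| Place | Period | What it governs |
|---|---|---|
| Study Summary | none given | primary endpoint |
| 8.2 | therapy plus 12 months | primary endpoint |
| 12.1, 12.2 | none given | adverse-event analysis |
| 13.1.4 | 30 days after treatment | adverse-event reporting |
| 13.1.7 | 6 months | events after leaving the study |
| 9.4.2 | 12 weeks | toxicity in withdrawn patients |
| 8.1, Table 3 | visits to Month 24 | scheduled follow-up |
| 13.2 | every contact; the study period | asking about and recording events |

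**2. Shares of follow-up**
- 30 days of the 12-month window: 30/365.25 = 8.2%.
- 30 days of 24 months: 30/730.5 = 4.1%.
- 12 months of 24 months: 12/24 = 50%.
- With 10 patients and complete follow-up: 10 × 1 = 10 patient-years over 12 months and 10 × 2 = 20 over 24 months.

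**3. The planned estimate.** Section 12.1 uses an exact binomial interval on patients. With 0 of 10 affected, the two-sided 95% upper limit is 1 − 0.025^(1/10) = 30.8%. The number of patients is the same for both windows, so the limit is too. Only the period it describes changes.

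**4. A rate per patient-year, which is not in the plan.** With no events in T patient-years, the one-sided 95% Poisson upper limit is −ln(0.05)/T ≈ 3.0/T: 3.0/10 = 0.30 and 3.0/20 = 0.15 per patient-year. This assumes a constant rate and no dropout.

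**5. Chance of at least one event in the window.** The documents give no event rate, so an assumed constant rate r per patient-year is varied: P = 1 − exp(−rT). For the 30-day period, T = 10 × 30/365.25 = 0.82.

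| Assumed r | 30 days (T = 0.82) | 12 months (T = 10) | 24 months (T = 20) |
|---|---|---|---|
| 2% | 2% | 18% | 33% |
| 5% | 4% | 39% | 63% |
| 10% | 8% | 63% | 86% |

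**The case against.** A 12-month primary window can be deliberate. It matches the 12-month efficacy objective in 7.2.2 and the 12-month feasibility endpoint in 8.3.1. Late events also have other safeguards: 13.2 requires immediate reporting of possibly related serious events after the study period, 13.1.7 asks for notification of later cancer, and the DSMB reviews event frequency and severity. This stands, and it is why the 12-month count should remain primary. These safeguards deal with reporting and oversight, however. They do not say which events enter the published safety result.

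Three stronger readings are tempting but unsupported.

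- *The plan excludes second-year events from its only adverse-event analysis.* That is an inference from 8.2. Section 12.1 states no cut-off, and 8.2 does not say that later events are dropped. The supported statement is that no analysis is assigned to them.
- *Every patient is monitored for adverse events to Month 24.* Section 13.2 points that way, but its study period is the term that 13.1.4 ties to 30 days. In the available text of Table 3 the entry for continuous monitoring cannot be matched to the adverse-event row with certainty. Collection over 24 months is therefore not settled.
- *A longer window makes the planned estimate more precise.* It does not, as step 3 of the working shows. The fall from 0.30 to 0.15 belongs to a rate that the plan does not use.

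The statement in 13.2 that no tumors were seen over 4 years is offered as reassurance. It does not show that the protocol regards late events as a concern, and the point does not rely on it.

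**Conclusion.** The point holds as an unreconciled set of adverse-event periods with a gap in the stated analysis. If 13.1.4 governs, required reporting ends about 11 months before the primary endpoint window closes. If 8.2 governs the analysis, the second half of planned follow-up has no stated safety summary.

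The gain from repair is coverage: second-year events would enter the reported safety result. The patient-year figures assume 10 treated patients with complete follow-up. The event probabilities also assume a constant rate after a single infusion, and the rates of 2% to 10% per year are illustrations. They show the chance that an event falls in the analysed window, not the chance that it goes unnoticed by the clinic.

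This should be corrected. It does not call for a different primary endpoint.

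**What to change.** 1. In 13.1.4, state one adverse-event collection period that covers at least the endpoint window and matches the scheduled visits to Month 24. Align the study period in 13.2, the adverse-event row of Table 3, the 6 months in 13.1.7 and the 12 weeks in 9.4.2 with it, or say why a different period applies.
2. In 8.2, keep the 12-month count with its exact 95% interval as primary. Put the same window in the Study Summary and in 12.1.
3. Add to 8.2 and 12.1: *Treatment-related adverse events and all serious adverse events with onset through the Month 24 visit will be tabulated as a secondary safety analysis, as the number of patients with at least one event (exact 95% CI) and as events per patient-year.*

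The cost is wording in the sections named, one extra table, and adverse-event recording at visits already scheduled. No visits or tests are added. If sites have been working to the 30-day period, they will need to be told of the longer one.

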6.1 Introduction

In Type 1 diabetes (T1D), autoimmune destruction of pancreatic islet β cells reduces an individual's ability to regulate blood glucose, ultimately resulting in poor blood circulation, heart disease, stroke, infection, renal failure, and often premature death. Each day, millions of patients with T1D receive insulin injections to survive, but these injections do nothing to address the underlying T cell-mediated autoimmune dysfunction. Ideally, therapeutic approaches for treating or curing T1D should address multiple or all of the underlying causes of autoimmunity in the disease. Unfortunately, the etiology of T1D in humans remains largely unknown. Possible contributors to the initiation or potentiation of autoimmunity in T1D include genetic, epigenetic, physical, social, and environmental factors [9,12]. As is expected in conditions with multiple contributing factors, T1D-related immune system dysfunction has been traced to dysfunctions in multiple cell types and targets including T cells, B cells, regulatory T cells (Tregs), monocytes/macrophages (Mo/M ϕ s), dendritic cells (DCs), natural killer (NK) cells, and natural killer T (NKT) cells [13]. Due to the polyclonal nature of T1D-related autoimmune responses and the global challenges of immune regulation in T1D patients, therapies and trials that target only one or a few components of the autoimmune response are likely to fail. A true cure has proven elusive despite intensive research pressure using conventional approaches over the past 30 years [14]. Several recent clinical trials [15,16] highlight the challenges in conquering T1D, but their failures provide some valuable lessons about the limitations of conventional immune therapy and the future direction of the quest. Specifically, they point to the need for an approach that produces comprehensive immune modulation at both the local pancreatic and systemic levels rather than targeting the pancreatic effects of one or a few components of the immune system. Stem Cell Educator (SCE) therapy takes this broader approach [1,5,10], which was developed by [name].

While traditional stem cell therapy is not likely to be effective for long-term treatment of T1D, recent studies suggest alternative approaches using stem cells may overcome the autoimmune component of the disease. Human cord blood-derived multipotent stem cells (CB-SCs) [1,2] and mesenchymal stem cells (MSCs) [3-5] have been shown to modulate immune activity *in vitro*. Subsequent studies have demonstrated that CB-SCs can be used to alter immune function and improve markers of T1D in nonobese diabetic (NOD) mice [6], and they can modulate the immune function of T1D patient-derived islet β cell-specific pathogenic T cell clones in co-culture [9]. Studies in an animal model also suggest that CB-SC treatment may allow the patient to regenerate the native population of islet β cells without stem cell transplantation [6,9,24].

To translate these findings into a clinically feasible therapy, [name] (currently working at Hackensack University Medical Center) developed the procedure of "SCE" therapy in which a patient's blood was circulated through a closed-loop system that separated lymphocytes from the whole blood and briefly co-cultured them with adherent CB-SCs before returning them to the patient's circulation [1]. In an open-label, phase1/phase 2 study conducted in China, patients (n = 15) with T1D received one treatment with the SCE. Findings from this study demonstrated the feasibility and safety of SCE therapy and demonstrated that T1D patients could achieve improved metabolic control and reduced autoimmunity that lasted months following a single treatment. Notably, our initial clinical data provided powerful evidence that reversal of autoimmunity could lead to regeneration of islet β cells and improvement of metabolic control in long-standing T1D subjects [1].

The SCE device is essentially a stack of specially-designed Petri dishes with tightly adherent CB-SCs cultured to confluence. In the closed-loop system, the patient's lymphocytes slowly pass through the device at a constant flow rate and can interact with the CB-SCs *in vitro*, and the cells returned to the patients are thus autologous lymphocytes that have been treated (or educated) by the CB-SCs. The SCE therapy required only two venipunctures, carried a lower risk of infection than a typical blood transfusion, and did not introduce stem cells or reagents into the patients. In addition, CB-SCs have very low immunogenicity, and the CB-SCs cultured in the device are a highly restricted population and contain no CD3+ T cells or other lymphocyte subsets, eliminating the need for human leukocyte antigen (HLA) matching prior to treatment [8,9,11]. This innovative approach has the potential to provide CB-SC-mediated immune modulation therapy for multiple autoimmune diseases while mitigating the safety and ethical concerns associated with other approaches [2,3,5]. The relative simplicity of the approach may also provide cost and time savings relative to other approaches.

Results from this initial Chinese trial confirmed prior studies indicating that the adherence of CB-SCs could be exploited to develop therapies that do not introduce the CB-SCs into the patient [1,6,9]. The improvement of islet β cell function in T1D patients with residual islet β cells is impressive, but the recovery of islet β cell function in T1D patients without evident β cell function prior to treatment suggested that SCE therapy could address the underlying challenge of autoimmunity and could control the immune response sufficiently to allow regeneration of the native β cell population. Thus, this trial provided initial evidence that exposing a patient's lymphocytes to CB-

SCs can achieve the two essential outcomes required to cure T1D: reversal of autoimmunity and regeneration of islet β cells [1,5].

